4.1 Inclusion Criteria

To be eligible for study participation, all of the following inclusion criteria must be met:

1. Must have given written informed consent (signed and dated).
2. Patient is ≥ 18 years old or age of majority in the country in which they reside, whichever is higher.
3. Recurrent/metastatic histologically or cytologically proven squamous cell carcinoma of the head and neck that is considered incurable by local therapy. Eligible primary tumor locations are oropharynx, oral cavity, hypopharynx, and larynx.
4. Presence of measurable tumor per RECIST v1.1 criteria.
5. Detectable PD-L1 expression in tumor, defined as CPS ≥ 1 determined by a test approved by US FDA or national regulatory agency of the country in which the patient resides. A TPS value ≥ 30 may be used for initial eligibility however a CPS value must be obtained and reported utilizing a tissue sample obtained prior to the start of study treatment.
 - Examples of approved tests include PD-L1 IHC 22C3 pharmDx (Dako North America, Inc.); PD-L1 IHC 28-8 pharmDx (Dako North America, Inc.); Ventana PD-L1 (SP142) Assay (Ventana Medical Systems, Inc.); Ventana PD-L1 (SP263) Assay (Ventana Medical Systems, Inc)
6. Baseline fresh tumor biopsy or archival specimen. A fresh biopsy is preferred if safe and feasible to obtain and consented to by the patient (details provided in section on **Tissue Samples [Section 7.12.1]**).
7. ECOG performance status of 0 or 1.
8. Adequate organ function within 10 days of study treatment, including the following:
 - a. Absolute neutrophil count $\geq 1,500/\mu\text{L}$
 - b. Platelet count $\geq 100,000/\mu\text{L}$
 - c. Hemoglobin $\geq 9 \text{ g/dL}$ (may be with transfusion)
 - d. Serum creatinine within normal limits or, for patients with serum creatinine above institutional normal:
 - Creatinine clearance $\geq 45 \text{ mL/min}$
 - Creatine clearance can be calculated using an appropriate standard formula (e.g. Modification of Diet in Renal Disease equation [MDRD], Cockcroft-Gault formula, or another formula that is typically used at the

-
- institution) or can be obtained from a 24-hour urine collection. ([Appendix 2](#))
- e. Total bilirubin $\leq 1.5 \times$ upper limit of normal (ULN)

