G1-2: Evidence of RBC destruction (schistocytosis) without clinical consequences of anemia, thrombocytopenia G2	
 • Continue pembrolizumab with close clinical follow-up and laboratory evaluation. • Supportive care.
G3: Laboratory findings with clinical consequences (e.g., renal insufficiency and petechiae) G4: Life-threatening consequences, (e.g., CNS thrombosis or embolism or renal failure)	
 • Permanently discontinue pembrolizumab. • Hematology consult. • Begin therapy with eculizumab (anti-C5 antibody) 900 mg weekly × 4 doses, 1,200 mg week 5, then 1,200 mg every 2 weeks. • Red blood transfusion according to existing guidelines.
Aplastic Anemia	
G1: Mild: >0.5 PMNs × 10 ⁹ /L hypocellular marrow, with marrow cellularity <25%, Peripheral platelet count >20,000, reticulocyte count >20,000	
 • Hold pembrolizumab and provide growth factor support, close clinical follow-up, and laboratory evaluation. • Supportive transfusions as per local guidelines.
G2: Moderate: Hypocellular marrow <25% and two of the following ANC <500, peripheral platelet <20,000 and reticulocyte <20,000	
 • Hold pembrolizumab and provide growth factor support and close clinical laboratory evaluations daily. • Hematology consult. • Administer horse ATG plus cyclosporine. • Supportive transfusions as per local guidelines. All blood products should be irradiated and filtered. • HLA typing and evaluation for bone marrow transplantation if patient is a candidate.

AE and Grade by CTCAE v5.0	Management
G3-4: Severe: ANC <200, platelet count <20,000, reticulocyte count of <20,000, plus hypocellular marrow <25%.	
 As per G2 Hold pembrolizumab and monitor weekly for improvement. If not resolved, discontinue treatment until AE has reverted to G1. If no response, repeat immunosuppression with rabbit ATG plus cyclosporine and cyclophosphamide. For refractory patients, consider eltrombopag plus supportive care.
Lymphopenia	

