All Grades	
 No specific action is required for lymphopenia G1-G3 and pembrolizumab therapy should be continued. For G4 (<250 PB lymphocyte count), continue pembrolizumab and initiate Mycobacterium avium complex prophylaxis and Pneumocystis jirovecii prophylaxis, CMV screening, HIV and hepatitis screening, if not already done. May consider EBV testing if evidence of lymphadenopathy or hepatitis, fevers, and hemolysis occur c/w lymphoproliferative disease occurs.
ITP	
G1: Platelet count 75 to <100/ μ L	
 Continue pembrolizumab with close clinical follow-up and laboratory evaluation.
G2: Platelet count 50 to <75/ μ L	
 Hold pembrolizumab but monitor for improvement. If not resolved, interrupt treatment until AE has reverted to G1. Administer prednisone 1 mg/kg per day (dosage range: 0.5–2 mg/kg per day) orally for 4 weeks followed by taper over 4-6 weeks to the lowest effective dose. IVIG may be used in conjunction with corticosteroids if a more rapid increase in platelet count is required.
G3: Platelet count 25 to <50/ μ L G4: Platelet count <25/ μ L	
 As per G2. Hematology consult. Consider as alternative to prednisone, dexamethasone 40 mg daily for 4 days. If IVIG is used, the dose should initially be 1 g/kg as a one-time dose. If previous treatment with corticosteroids and/or IVIG has been unsuccessful, subsequent treatment may include rituximab, thrombopoietin receptor agonists, or more potent immunosuppression.

AE and Grade by CTCAE v5.0	Management
Acquired Hemophilia A	
G1: Mild: 5%-40% of normal factor activity in blood; 0.05-0.4 IU/mL of whole blood	
 Hold pembrolizumab and discuss resumption with patient only after taking into account the risks and benefits. Administer 0.5-1 mg/kg/d prednisone. Transfusion support as required. Treatment of bleeding disorders with hematology consult.

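### The ITP platelet bands in Protocol Appendix 4 are printed per microlitre without the ×1,000 factor

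*Protocol*

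**What the plan says.** Protocol Appendix 4, under Hematologic Toxicities, gives three ITP rows covering four grades, each with the count per microlitre:

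- "G1: Platelet count 75 to <100": continue pembrolizumab with close follow-up.
- "G2: Platelet count 50 to <75": "Hold pembrolizumab but monitor for improvement", with prednisone, and IVIG if a faster rise is needed.
- "G3: Platelet count 25 to <50" and "G4: Platelet count <25", sharing one row: as for Grade 2, plus a hematology consult and further options.

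The column header is "AE and Grade by CTCAE v5.0". Neither the header nor the table's footnote supplies a factor of 1,000.

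Elsewhere the protocol uses full platelet counts. Section 4.1, item 8b (repeated in the synopsis) requires a "Platelet count" of at least 100,000 per microlitre. In the same appendix, the aplastic anemia Grade 1 row uses "Peripheral platelet count >20,000", and the higher grades there use a cut-off of <20,000. No unit is printed for those.

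**The concern.** These cells place a threshold beside an action: hold pembrolizumab, start prednisone, call hematology. Taken at face value, no realistic platelet count would reach them.

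Pembrolizumab is given in both arms. Section 5.4.1 names thrombocytopenia as a possible overlapping side effect of the two drugs, and Section 1.1.2 lists it among the risks seen with danvatirsen, so a site has reason to consult these rows. Section 5.4.3 offers the appendix as a quick reference, and its printed limits should therefore be usable as they stand.

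What is at stake is patient management, not the statistics.

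**Working it through.** The plan computes nothing from these bands, so there is no figure to reproduce. The check is a comparison of units.

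**Inputs**
- ITP limits, Appendix 4: 100, 75, 50 and 25 per microlitre (upper limits of Grades 1 to 4).
- Eligibility floor, Section 4.1 item 8b: 100,000 per microlitre.
- Aplastic anemia cut-off, Appendix 4: 20,000 (no unit printed).

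**Step 1. The gap that the documents show directly.** Same analyte, same printed unit: 100,000 / 100 = 1,000. With a ×1,000 factor, the Grade 1 upper limit equals the eligibility floor exactly.

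**Step 2. The other three limits.** 75, 50 and 25 have no comparator with a printed unit. They run on continuously from the Grade 1 band, so the same factor is inferred. The 20,000 cut-offs in the aplastic anemia rows fit that scale.

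**Step 3. What a literal reading does.** A patient with 20,000 platelets per microlitre is above 100, the top of Grade 1, and receives no ITP grade. With the factor restored, 20,000 is below 25,000 and is Grade 4.

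**Step 4. Fall needed from the 100,000 floor to the upper limit of each grade.** The formula is 1 − limit / 100,000.

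| Grade | As printed | With ×1,000 |
|---|---|---|
| G2 | 1 − 75/100,000 = 99.925% | 1 − 75,000/100,000 = 25% |
| G3 | 1 − 50/100,000 = 99.95% | 1 − 50,000/100,000 = 50% |
| G4 | 1 − 25/100,000 = 99.975% | 1 − 25,000/100,000 = 75% |

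**Step 5. Could the factor have been lost when the PDF was read?** This is unlikely. The per-microlitre unit survives in all four bands. A ×10⁹/L multiplier survives in the neighbouring aplastic anemia Grade 1 row, and three parallel hemoglobin unit systems survive in the hemolytic anemia rows. The same factor would have had to vanish four times while the text around it stayed intact. It cannot be fully excluded.

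**The case against.** The strongest reply is that this is a typographical slip which the protocol already contains.

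- **Grading.** The table header and Section 7.9.3 both grade by CTCAE v5.0, so a site can find the right row by grade without using the printed count. The acquired TTP rows in the same appendix cite thrombocytopenia by grade alone.
- **Precedence.** Section 5.4.3 directs sites to the ASCO guideline and says Appendix 4 does not replace it.
- **Escalation.** Section 5.4.1 sends questions about overlapping toxicities to the Medical Monitor at once.
- **Danvatirsen.** Thrombocytopenia attributed to danvatirsen is managed by grade in Table 3.
- **Reporting.** SAP Section 5.13.2 grades laboratory values programmatically by CTCAE v5.0, so the slip does not reach the reported grades.
- **Comparator.** Inclusion 8b is an eligibility floor, and nothing in the documents says the Grade 1 limit must equal it.
- **Plausibility.** The percentage falls in Step 4 describe a reading that no clinician would adopt.
- **Timing.** SAP Section 9 records early termination, and the documents do not show that any patient remains on pembrolizumab.

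Most of this stands, and it is why the point ranks low. It is a unit error, not a faulty calculation. The percentages show what the literal text implies; they do not estimate harm. The comparator is indirect, but a band for a mild fall in platelets cannot sensibly lie 1,000-fold below the count at which patients enter. None of these points makes the printed thresholds correct.

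**Conclusion.** The point holds as a minor unit error. One limit is shown to be out of scale by a factor of 1,000 against the protocol's own eligibility figure. The other three are inferred to share the omission. Three table cells are affected.

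The conclusion assumes that the published text reflects the original layout, and that the four bands were meant to be on one scale. Both are very likely.

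Practical risk is small because of the safeguards above. Eligibility, sample size, power, error rates and all planned analyses are untouched. The correction is worth making if the opportunity arises; it is not a condition for accepting the plan.

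**What to change.** Restate the three cells per microlitre as:

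- Grade 1: 75,000 to <100,000
- Grade 2: 50,000 to <75,000
- Grade 3: 25,000 to <50,000, with Grade 4 (same cell): <25,000

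Alternatively, keep the printed numbers and change the unit to ×10⁹/L. Check the corrected cells against the source guideline before release.

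The cost is a clarification letter to approximately 35 sites, or one line in the next amendment if there is one. Given early termination, the benefit is confined to any patients still on pembrolizumab and to any later protocol that reuses this appendix. If no patient remains on treatment, correcting the template is enough.

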
APPENDIX 5. RECIST V. 1.1

Measurable Disease. Measurable tumor lesions (nodal, subcutaneous, lung parenchyma, solid organ metastases) are defined as those that can be accurately measured in at least one dimension (longest diameter to be recorded) as ≥ 20 mm with chest X-ray and as ≥ 10 mm with computed tomography (CT) scan or clinical examination. Bone lesions are considered measurable only if assessed by CT scan and have an identifiable soft tissue component that meets these requirements (soft tissue component ≥ 10 mm by CT scan). ***Malignant lymph nodes*** must be ≥ 15 mm in the short axis to be considered measurable; only the short axis will be measured and followed. All tumor measurements must be recorded in millimeters (or decimal fractions of centimeters). Previously irradiated lesions are not considered measurable unless progression has been documented in the lesion.

Non-Measurable Disease. All other lesions (or sites of disease), including small lesions are considered non-measurable disease. Bone lesions without a measurable soft tissue component, leptomeningeal disease, ascites, pleural/pericardial effusions, lymphangitis cutis/pulmonis, inflammatory breast disease, lymphangitic involvement of lung or skin, and abdominal masses followed by clinical examination are all non-measurable. Lesions in previously irradiated areas are non-measurable, unless progression has been demonstrated.

Target Lesions. When more than one measurable tumor lesion is present at baseline all lesions up to a maximum of 5 lesions total (and a maximum of 2 lesions per organ) representative of all involved organs should be identified as target lesions and will be recorded and measured at baseline. Target lesions should be selected on the basis of their size (lesions with the longest diameter), be representative of all involved organs, but in addition should be those that lend themselves to reproducible repeated measurements. Note that pathological nodes must meet the criterion of a short axis of ≥ 15 mm by CT scan and only the short axis of these nodes will contribute to the baseline sum. All other pathological nodes (those with short axis ≥ 10 mm but < 15 mm) should be considered non-target lesions. Nodes that have a short axis < 10 mm are considered non-pathological and should not be recorded or followed. At baseline, the sum of the target lesions (longest diameter of tumor lesions plus short axis of lymph nodes: overall maximum of 5) is to be recorded. After baseline, a value should be provided on the case report form for all identified target lesions for each assessment, even if very small. If extremely small and faint lesions cannot be accurately measured but are deemed to be present, a default value of 5 mm may be used. If lesions are too small to measure and indeed are believed to be absent, a default value of 0 mm may be used.

Non-Target Lesions. All non-measurable lesions (or sites of disease) plus any measurable lesions over and above those listed as target lesions are considered *non-target lesions*. Measurements are not required but these lesions should be noted at baseline and should be followed as “present” or “absent.”

Response.

All patients will have their BEST OBJECTIVE RESPONSE from the start of study treatment until the end of treatment classified as outlined below:

Complete Response (CR): disappearance of target and non-target lesions and normalization of tumor markers. Pathological lymph nodes must have short axis

measures <10 mm (note: continue to record the measurement even if <10 mm and considered CR). Residual lesions (other than nodes <10 mm) thought to be non-malignant should be further investigated by cytology specialized imaging or other techniques as appropriate for individual cases before CR can be accepted. Confirmation of response is required and should occur no less than 4 weeks after the initial response.

Partial Response (PR): at least a 30% decrease in the sum of measures (longest diameter for tumor lesions and short axis measure for nodes) of target lesions, taking as reference the baseline sum of diameters. Non-target lesions must be non-PD. Confirmation of response should occur no less than 4 weeks after the initial response.

Stable Disease (SD): Neither sufficient shrinkage to qualify for PR nor sufficient increase to qualify for PD taking as reference the smallest sum of diameters on study.

Progressive Disease (PD): at least a 20% increase in the sum of diameters of measured lesions taking as references the smallest sum of diameters recorded on study (including baseline) AND an absolute increase of ≥ 5 mm. Appearance of new lesions will also constitute PD (including lesions in previously unassessed areas). In exceptional circumstances, unequivocal progression of non-target disease may be accepted as evidence of disease progression, where the overall tumor burden has increased sufficiently to merit discontinuation of treatment or where the tumor burden appears to have increased by at least 73% in volume. Modest increases in the size of one or more non-target lesions are NOT considered unequivocal progression. If the evidence of PD is equivocal (target or non-target), treatment may continue until the next assessment, but if confirmed, the earlier date must be used.

Integration of Target, Non-Target, and New Lesions into Response Assessment

Target Lesions	Non-Target Lesions	New Lesions	Overall Response	Best Response for This Category Also Requires
Target lesions \pm non-target lesions				
CR	CR	No	CR	Normalization of tumor markers, tumor nodes <10 mm
CR	Non-CR/Non-PD	No	PR	
CR	Not all evaluated	No	PR	
PR	Non-PD/not all evaluated	No	PR	
SD	Non-PD/not all evaluated	No	SD	Documented at least once ≥ 4 wks. from baseline
Not all evaluated	Non-PD	No	NE	
PD	Any	Any	PD	
Any	PD	Any	PD	
Any	Any	Yes	PD	
Non-target lesions ONLY				
No target	CR	No	CR	Normalization of tumor markers, tumor nodes <10 mm
No target	Non-CR/non-PD	No	Non-CR/non-PD	
No target	Not all evaluated	No	NE	

Flamingo Therapeutics

Activity and Safety of Danvatirsen and Pembrolizumab in HNSCC

8 May 2025

Trial ID: FLM-6774-201

Amendment 4

Target Lesions	Non-Target Lesions	New Lesions	Overall Response	Best Response for This Category Also Requires
No target	Uequivocal PD	Any	PD	
No target	Any	Yes*	PD	

Note: Patients with a global deterioration of health status requiring discontinuation of treatment without objective evidence of disease progression at that time should be reported as "symptomatic deterioration." This is a reason for stopping therapy, but is NOT objective PD. Every effort should be made to document the objective progression even after discontinuation of treatment.

*Investigators should record all new lesions; if the new lesion is felt to be equivocal, treatment may be continued pending further assessments.

Abbreviations: CR = complete response; NE = not evaluable; PD = progressive disease; PR = partial response; SD = stable disease.

## LIST OF ABBREVIATIONS

Abbreviation	Definition
ADA	Anti-drug Antibody
AE	Adverse Event
BOP2	Bayesian optimal phase 2
BLQ	Below the Limit of Quantitation
BOR	Best Overall Response
CI	Confidence Interval
CPS	Combined Positive Score
CR	Complete Response
CRR	Complete Response Rate
CSR	Clinical Study Report
CTCAE	Common Terminology Criteria for Adverse Events
DCR	Disease Control Rate
DOR	Duration Of Response
ECG	Electrocardiogram
ECOG	Eastern Cooperative Oncology Group
eCRF	Electronic Case Report Form
EOT	End Of Treatment
FAS	Full Analysis Set
FDA	Food and Drug Administration
HNSCC	Head And Neck Squamous Cell Carcinoma
HPV	Human Papillomavirus
ICF	Informed Consent Form
IRT	Interactive Response Technology
IV	Intravenous
MedDRA	Medical Dictionary for Regulatory Activities
NA	Not Applicable

### Confidentiality Statement

This document is the property of Worldwide Clinical Trials Inc. and may not be duplicated, copied, altered or removed from company without prior approval from Worldwide Quality Assurance or in compliance with Worldwide Standard Operating Procedures.

Worldwide Clinical Trials Controlled Quality Management Document			
 WORLDWIDE CLINICAL TRIALS	Sponsor:	Flamingo Therapeutics	
	Protocol Number:	FLM-6774-201	
STATISTICAL ANALYSIS PLAN			

Abbreviation	Definition
NE	Not Evaluable
NCI	National Cancer Institute
ORR	Objective Response Rate
OS	Overall Survival
PBMC	Peripheral Blood Mononuclear Cell
PCR	Polymerase Chain Reaction
PD	Progressive Disease
PD-L1	Programmed Death-Ligand 1
PFS	Progression-Free Survival
PK	Pharmacokinetic
PR	Partial Response
PT	Preferred Term
QTc	Corrected QT Interval
RECIST v1.1	Response Evaluation Criteria in Solid Tumors Version 1.1
SAE	Serious Adverse Event
SAP	Statistical Analysis Plan
SD	Stable Disease
SOC	System Organ Class
TEAE	Treatment-Emergent Adverse Event
TFL	Tables, Figures and Listings

## 1 INTRODUCTION

This document details the planned statistical analyses of Flamingo Therapeutics protocol FLM-6774-201, titled “An Open-Label, Phase II, Randomized, Controlled Study of Danvatirsen Plus Pembrolizumab Compared to Pembrolizumab Alone in Recurrent or Metastatic Head and Neck Squamous Cell Carcinoma (HNSCC)”.

The proposed analyses are based on the contents of the protocol amendment 4.0 dated 05 – May 2025.

This is a Phase II, open-label, randomized study. The study consists of a screening period, treatment period, safety follow-up, and survival follow-up. Treatment cycles are based on the schedule of administration of pembrolizumab. Each cycle is considered 21 days in length. The maximum duration of treatment with pembrolizumab is 24 months. There will be no limit on the duration of treatment with Danvatirsen.

This Statistical Analysis Plan (SAP) will only detail analyses for safety and efficacy of the study. Detail of pharmacokinetic and biomarker analyses, unless otherwise noted, are outside the scope of this document and will be handled separately.

QMD Ref: Worldwide-TMP-ST-054-1.0_Effective: 12Aug2022	Governing QMD: Worldwide-SOP-ST-026
Confidentiality Statement	

This document is the property of Worldwide Clinical Trials Inc. and may not be duplicated, copied, altered or removed from company without prior approval from Worldwide Quality Assurance or in compliance with Worldwide Standard Operating Procedures.

Worldwide Clinical Trials Controlled Quality Management Document			
 WORLDWIDE CLINICAL TRIALS	Sponsor:	Flamingo Therapeutics	
	Protocol Number:	FLM-6774-201	
STATISTICAL ANALYSIS PLAN			

## 2 STUDY OBJECTIVES AND ENDPOINTS

### 2.1 Objectives and Endpoints

Study Objects and Endpoints	
Primary Objectives	Primary Endpoints

 
To determine the objective response rate (ORR) by Response Evaluation Criteria in Solid Tumors version 1.1 (RECIST v1.1) as determined by the Investigator for the combination of danvatirsen and pembrolizumab compared with pembrolizumab alone as first-line treatment of patients with metastatic or unresectable, recurrent HNSCC whose tumors express programmed death-ligand 1 (PD-L1) by Combined Positive Score (CPS) <math>\geq 1</math>.
 
	
 
Confirmed ORR (partial response [PR] + complete response [CR] defined according to RECIST v1.1) (Eisenhauer et al 2009)
 

Secondary Objectives	Secondary Endpoints

 
To characterize the safety and tolerability of the combination of danvatirsen and pembrolizumab
 
To evaluate additional efficacy parameters for the combination of danvatirsen and pembrolizumab compared with pembrolizumab alone
 
To characterize the pharmacokinetics (PK) of danvatirsen
 
To determine the immunogenicity of danvatirsen
 
	
 
Adverse events (AEs), serious adverse events, physical examinations, clinical laboratory values, and tolerability (dose interruptions/reductions)
 
Duration of response (DOR) by RECIST v1.1
 
Disease control rate (DCR) and CR rate by RECIST v1.1
 
ORR and DOR by RECIST v1.1 in tumors with CPS <math>\geq 20</math> and <math>\geq 50</math>
 
Progression-free survival (PFS) by RECIST v1.1, defined as the time from randomization to the first documentation of progressive disease (PD) or death from any cause, whichever comes first
 
Overall survival (OS), defined as time from randomization to death from any cause
 
PK parameters derived from plasma concentrations of danvatirsen at defined timepoints in the combination regimen
 
Anti-danvatirsen antibody titers at defined timepoints in the combination regimen.
 

